4.1.1.12. Laboratory values

Laboratory values below the lower limit of quantification (LLOQ) will be set to ½*LLOQ. For values above upper limit of quantification values will be set to that limit.

4.1.1.13. Prior and concomitant medication

Prior medications are those with an end date of administration prior to the date of the first IMP administration.

Concomitant medications are those that started or continued during the study treatment period.

4.1.1.14. Pharmacokinetic parameters

PK parameters to be estimated according to the protocol:

- AUC_(0-24h): The area under the curve of plasma concentration vs time, from time point zero up to the time 24h after administration, unit: [ng*h/mL]. AUC_(0-24h) will be calculated according to the linear trapezoidal rule using actual sampling times and extrapolated basing on Kel if concentration at 24 h is below LLOQ.
- C_{max}: Maximum plasma concentration, unit: [ng/mL]. C_{max} defines the maximum concentration of the drug substance in plasma during dosing period. C_{max} will be obtained directly from the measured concentrations.
- AUC_(0-inf): The area under the curve of plasma concentration vs time, from time point zero extrapolated to infinity, unit: [ng*h/mL]. AUC_(0-inf) = AUC_(0-t) + C_t /K_{el}, C_t is the last measurable analyte concentration in plasma and K_{el} is the terminal elimination rate constant.
- t_{max}: Time to reach maximum plasma concentration, unit: [h]. The t_{max} will be obtained directly from the actual sampling times.
- K_{el}: Terminal elimination rate constant, unit: [1/h]. K_{el} will be estimated via linear regression of time versus log of concentration. This parameter will be calculated by linear least squares regression analysis using at least last three non-zero plasma concentration values. C_{max} values will not be included in K_{el} calculation. K_{el} will only be calculated if the adjusted coefficient of determination of exponential fit (R² adjusted) is not less than 0.7 (R² ≥ 0.7).
- t_{1/2}: Plasma elimination half-life, unit: [h]. The t_{1/2} will be calculated as 0.693/K_{el}.
- CL/F: apparent systemic clearance, calculated as dose administered in dosing interval divided by AUC_(0-inf) on Day 1 or divided by AUC_(0-tau).
- Vz/F: apparent volume of distribution; a hypothetical volume of fluid into which the drug is dispersed. It is calculated as Dose/(K_{el}*AUC_(0-inf)) for Day 1 and Dose/(K_{el}*AUC_(0-tau)) for Day 7.
- C_{trough}: the trough concentration is the concentration reached by the drug immediately before the next dose is administered as well as 24 h after the last dose administration.

4.1.2. Specifications for summary tables

For **continuous variables**, summary statistics will generally consist of sample size N, number of missing values, arithmetic mean, standard deviation (SD), median, lower and upper quantile, minimum, and maximum. Summaries of PK variables (if data transformation is necessary) will, in addition, contain the geometric mean and the coefficient of variation.

Binary/categorical variables will be summarized and displayed in frequency tables showing sample size, absolute and relative frequencies.

In general, data will be included in summary tables stratified by randomized treatment group.

4.1.3. Specifications for plots

Unless otherwise specified, plots related to continuous endpoints will take form of a bar representing LS means calculated from MMRM model and whiskers representing confidence interval. Binary endpoints will take form of a forest plot – point representing proportion of subjects meeting the endpoint and whiskers representing confidence interval.

Results from logistic regression will also take form of a forest plot – point with whiskers, where point represents odds ratio and whiskers confidence interval.

Depending on assessment of variable distribution (on basis of Q-Q plot), safety data will be presented as line and point and whisker plots (for normally distributed values) or boxplots (where there is a notable skewness of variable distribution). For line and point and whisker plots, the points will represent the mean value and whiskers – standard deviation of the mean. For boxplot top and bottom of the box will represent lower and upper quartile respectively. Thick line in the middle of the box will be median. Whiskers will represent the lowest value at most Q1-1.5*IQR (inter quantile range) and the largest value no further than Q3+1.5*IQR. Points will represent potential outliers.

Data will be shown for each randomized treatment group. Data collected during unscheduled visit will not be shown on plots unless otherwise specified.

4.1.4. Data listings

Data on listings will be listed as documented. Relevant generated and transformed variables will be listed next to the original data items. Any imputed value will be flagged.

In all listings the patient identifier and the randomized treatment group will be included. The patient identifier consists of the center and the patient number, additionally a flag specifying analysis set will be provided.

In general, patient listings will be sorted by patient identifier and visit (if applicable), unless otherwise stated.

Patient listings of data that is collected independently from visits (e.g. adverse events, medical histories or medication) will be sorted by patient identifier, day of onset or start day of administration, duration and MedDRA preferred term or base substance name, respectively.

Missing values in the listings will be represented as NA (not available) for both text and numerical data. In case of partially missing dates (when day or day and month is unknown) missing data will be represented as series of 9s – for example 2023-03 will be presented as 2022-03-99. Any imputed data will be presented separately from raw data or flagged accordingly in order to be able to review all data as collected.

4.1.5. Handling of withdrawals, missing values and outliers

For the main analyses performed using the FAS and PP population, data will be analyzed as observed during the study, no imputation rule will be applied. For continuous endpoints measured longitudinally, the missing values post baseline will be handled in a mixed model for repeated measures, where the values are assumed to be missing at random. For binary endpoints values will be used as observed – excluding any missing values from analysis.

A sensitivity analysis will be conducted for primary and secondary efficacy endpoints, whereby missing data are imputed using multiple imputation (MI) for continuous endpoints and non-responder imputation (NRI) method for binary endpoints. For multiple imputation R seed will be set as 500036.

A worst-case scenario will be used in the estimation of partial dates for adverse events and concomitant medications. That is, for an incomplete start date the first day of the month or the first month of the year will be used. For an incomplete stop date the last day of the month or the last month of the year will be used. If an estimated start date of an adverse event is earlier

than the date of day 1 or the start date is completely missing, day 1 will be used, unless documented data does not allow for this interpretation.

Whenever estimated dates will be calculated, the incomplete date will be listed and the study day will be calculated using the estimated date. These study days will be flagged as estimated in listings.

In other situations missing data will generally not be replaced or imputed unless otherwise specified in this document.

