The 02PDE2019 study is considered a short term study with up to 7 days of medication washout period and 28-day treatment phase. The CPL500036 compound will be used in monotherapy, so other antipsychotic treatments will be discontinued, what is in line with the EMA guidelines which states that "treatments that may augment the test treatment should be excluded, despite the consequences of these exclusions for generalizability of the trial results. Therefore other antipsychotic drugs should be discontinued (...)" [30]. The protocol has been designed to minimize the risk to all research participants. This study will be performed in controlled settings, all patients will be hospitalized to assure patients safety. Subjects will be monitored to detect AEs during the study and followed appropriately to ensure resolution of AEs.

To manage potential side effects and symptoms that may occur, allowed treatments are described. During the study lorazepam may be administered for anxiety/agitation or to aid sleep. To manage insomnia from z-drugs, use of zolpidem is allowed in the study. To treat extrapyramidal side effects and akathisia benzatropine/biperiden and propanolol are permitted, respectively. The daily and weekly limits of those medications that can be used, on a PRN (as needed) basis are provided (rules for medication administration in Section 5.4.3). If a patient's condition will require to exceed the specified dose, it must be recorded as Serious Adverse Event.

During the whole study all the patients will be closely observed by the Investigator or appointed staff members to assure maximal safety. Safety is to be ensured by performing clinical assessments/ evaluations and clinical laboratory measurements/ evaluations. This includes i.a. monitoring of vital signs with 3-positional blood pressure and pulse measurements, ECG measurements and extrapyramidal side effects monitoring using Extrapyramidal Symptom Rating Scale (ESRS) assessments. Patients at imminent risk of suicide or injury to self, others, or property or participants who within the past year prior to screening have attempted suicide will be excluded from the study and risk of potential suicide ideations occurrence will be assessed during the study.

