5.4.3. Prior and Concomitant Treatments

Medication restrictions applicable before dosing are described in Section 5.3 (exclusion criteria). Prior medication will be recorded.

Any medicinal product, prescribed or over-the-counter (OTC), taken by a subject other than the IMP, is considered concomitant medication. Permitted medication (for prolonged use) includes only paracetamol in recommended doses (≤ 2 g per day) after approval by the Investigator or designee. Higher doses of paracetamol, up to 4 g per day may be given at the discretion of the

Investigator or designee to treat AEs such as fever and headache (only for short terms issues). Any concomitant treatment will be given only if deemed strictly necessary by the Investigator or designee. Use of concomitant medication will be recorded and reported.

Allowed concomitant medications taken by the patient in fasting conditions can be taken consistently with the current recommendations, but at least 1 hour interval between concomitant medication and IMP administration must be maintained with IMP taken as first.

Starting on the first day of Screening Period and as applicable, all antipsychotic or other psychotropic medications will be stopped with clinically appropriate titration down as per Investigator clinical judgment. Thereafter, patients will be instructed not to take any medications during the conduct of the study unless approved by the Investigator. Any patient who is unable to be safely discontinued from current antipsychotic therapy or other psychotropic medications will not be eligible for the study (see Section 7).

Medication history (psychotropic medication history during the previous 5 years and all other medications during the past 12 months) will be recorded at Screening (Visit 1) in the eCRF. Thereafter, any changes in concomitant medications or new medications added will be recorded in the eCRF.

Patients will not be eligible for the study if they have used any depot antipsychotic within 1 month (30 days) prior to Screening. The using of mianserin, mirtazapine, nefazadone, cyproheptadine, or fluvoxamine within 1 month (30 days) before Screening is not recommended.

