10.9. Prior and Concomitant Medication and Drug Administration

Prior medications are those that started and stopped prior to the first dose of IMP. Concomitant medications are those taken after first dosing (including medications that started prior to dosing and continued after).

Prior and concomitant medication will be classified using the ATC codes contained in Register of Medicinal Products Approved for Marketing on the territory of the Republic of Poland and listed by subject and will include the following information: reported name, preferred term, ATC level 2 (therapeutic subgroup) and 4 (chemical subgroup), the route of administration, dose, frequency, start date/time, duration and indication. Summary of prior and concomitant medications will be provided as a count and frequency for ATC level 2 and 4.

.

Drug administration dates and times will be listed for each subject.

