4.5. Concomitant medication

Prior and concomitant medications will be classified using the ATC codes contained in Register of Medicinal Products Approved for Marketing on the territory of the Republic of Poland¹. Summary of concomitant medications will be provided as count and frequency for ATC level 2 (therapeutic subgroup) and 4 (chemical subgroup). Listings of prior and concomitant medications will be provided and sorted by site, patient number, name of active substance, and date of last administration (if known).

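### Medication stop dates imputed to month or year end have no limit at first dose, so a psychotropic documented as already stopped can be tabulated as concomitant; the SAP also drops the protocol's prior-medication summary

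*SAP*

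**What the plan says.** SAP 4.1.5 sets a common rule for partial dates: "A worst-case scenario will be used in the estimation of partial dates for adverse events and concomitant medications". For stop dates: "For an incomplete stop date the last day of the month or the last month of the year will be used". The section adds that the study day is then calculated from the estimated date. SAP 4.1.1.1 names the split between earlier and concomitant medications as one use of the study day. SAP 4.1.1.13 draws the line: "Prior medications are those with an end date of administration prior to the date of the first IMP administration". Drugs that start or continue in the treatment period are concomitant.

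The only limit at Day 1 in SAP 4.1.5 concerns adverse event start dates ("If an estimated start date of an adverse event is earlier" than Day 1, Day 1 is used). The exception for contradicting documented data belongs to that same sentence. Neither is extended to medication stop dates.

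On the design side, Protocol 5.4.3 states: "Medication history (psychotropic medication history during the previous 5 years and all other medications during the past 12 months) will be recorded at Screening". Protocol 2.5 states: "The CPL500036 compound will be used in monotherapy, so other antipsychotic treatments will be discontinued".

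On reporting, Protocol 10.9 states: "Summary of prior and concomitant medications will be provided as a count and frequency for ATC level 2 and 4". SAP 4.5 states: "Summary of concomitant medications will be provided as count and frequency for ATC level 2" and level 4; prior medications are only listed. SAP 3.4 gives changes from the protocol as not applicable.

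**The concern.** Read in sequence, the SAP sections carry an imputed stop date into the prior/concomitant split with nothing to hold it before first dose. Suppose a site records at Screening that an antipsychotic was stopped earlier that year, month unknown. The rule sets the stop to the end of December, after first dose, and SAP 4.1.1.13 no longer allows the drug to be prior. Yet a drug already stopped at Screening cannot have continued into treatment.

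Antipsychotics are the class where this matters most. Protocol Table 9 allows them neither episodically nor chronically, so an entry in the by-arm concomitant table reads as prohibited use in a monotherapy trial.

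The missing prior-medication summary is a separate matter and does not depend on dates. Without it, and with no prior antipsychotic use among the baseline characteristics in SAP 4.3, pre-trial antipsychotic exposure is not tabulated by arm anywhere.

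**Working it through.** The plan gives no figure on this point, so there is none to reproduce. The check applies the rule as written.

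**Inputs.** Imputation to month end or to 31 December (SAP 4.1.5); prior only if the end date is before the first-dose date (SAP 4.1.1.13). Assumption: first-dose dates are uniform over a 365-day year. Let g be the number of calendar days from the true stop to first dose. The protocol has a Day 0 between Day -1 and Day 1, so Day -1 is g = 2 and Day -10 is g = 11.

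**Condition.** The imputed stop falls on or after first dose exactly when the true stop lies in the same month as first dose (month-only date) or the same year (year-only date).

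**Formulas.** In a month of L days, L − g first-dose days meet the condition, and none if g ≥ L.
- Month-only: M(g) = Σ max(L − g, 0) / 365 over the 12 months.
- Year-only: Y(g) = max(365 − g, 0) / 365.

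**Single gaps.**

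| g (days) | Month-only | Year-only |
|---|---|---|
| 7 | (365 − 84)/365 = 77.0% | 358/365 = 98.1% |
| 21 | (365 − 252)/365 = 31.0% | 344/365 = 94.2% |
| 30 | 7/365 = 1.9% | 335/365 = 91.8% |
| 31 | 0% | 334/365 = 91.5% |
| 90 | 0% | 275/365 = 75.3% |
| 180 | 0% | 185/365 = 50.7% |

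A complete stop date gives 0% at every gap. A stop more than 12 months before first dose cannot fall in the same calendar year, so it gives 0% even when only the year is known.

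**Averages over ranges of g, each day equally likely.**
- Previous 12 months (g = 2 to 365, 364 values). Year-only: the mean of 363, 362, …, 0 is 181.5, and 181.5/365 = 49.7%. Month-only: each month contributes (L − 1)(L − 2)/2, which is 435, 406 and 351 for 31, 30 and 28 days. The total is 7 × 435 + 4 × 406 + 351 = 5,020, and 5,020/(364 × 365) = 3.8%.
- Previous 60 days (g = 2 to 60, 59 values). Month-only: 5,020/(59 × 365) = 23.3%. Year-only: (365 − 31)/365 = 91.5%.
- Day -10 to Day -1 (g = 2 to 11, mean 6.5). Month-only: (365 − 12 × 6.5)/365 = 78.6%. Year-only: (365 − 6.5)/365 = 98.2%.

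These are shares of records that already have a partial stop date. The overall number misclassified cannot be computed, because the documents do not give the frequency of partial dates.

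**Where a limit must sit.** Take a true stop of 8 March recorded as March only, with first dose on 15 March. As written, the imputed stop is 31 March and the drug is not prior. Limited to the first-dose date it is 15 March, which is still not before first dose. Limited to the day before it is 14 March, and the drug is prior. By contrast, a 20 February stop recorded as February only is imputed to 28 February and is prior without any change.

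**Table coverage.** Protocol 10.9 has prior and concomitant medications summarised at ATC levels 2 and 4. SAP 4.5 has only concomitant medications summarised at those levels. SAP 3.4 records no change. The three statements cannot all stand.

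**The case against.** The strongest objection is one of scope. SAP 4.1.5 applies the worst-case rule to adverse events and concomitant medications, does not name prior medications, and says that missing data are generally not imputed elsewhere. A drug documented as stopped before first dose is prior under Protocol 10.9 and so might never reach the rule. This stands in part: it shows that the order of imputation and classification is unstated. It does not remove the gap. When the missing part of a date spans first dose, status cannot be read from the date until it is resolved. If imputation comes first, the drug turns concomitant; if classification comes first, the SAP gives no rule for it. Either way a sentence is needed.

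Second, a reader might take the 79% and 98% for stops on Day -10 to Day -1 as the size of the problem. The documents do not support that. Those stops occur from Screening onward under the investigator's judgment, washout is spent in the Clinical Unit, and Protocol 11.2 provides completeness checks and queries. Partial dates are least likely there, although the documents do not say so outright. They are more plausible in older history, where month-only dates do almost no harm.

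Third, counting an uncertain drug as concomitant is a declared conservative convention. That stands for drugs whose status is unknown, and the fix leaves it alone. It is not a reason to override a record that the drug had stopped.

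Fourth, SAP 4.1.4 and 4.1.5 keep partial dates visible and flag estimated values. That also stands, but the flags are promised for listings, not for the frequency table in SAP 4.5. Likewise, listing prior drugs with the randomised group softens the loss of the summary but does not replace it.

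**Conclusion.** The gap is real and minor. A psychotropic documented as stopped before first dose can be counted as concomitant, but only if the stop date is incomplete and its missing part spans first dose. In the most plausible case, a year-only entry in the psychotropic history with a stop in the previous 12 months, about half of such records are affected. For month-only records over the same window the figure is about 4%. Both rest on uniform first-dose dates, stop dates spread evenly over the window, and imputation applied before classification. The number of partial dates is unknown.

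The consequence is a distorted descriptive table by arm. Two stronger readings are tempting. One is that pre-treatment antipsychotics will generally appear as concomitant and so undermine the monotherapy design; the documents do not support this, since complete dates, and month-only dates from a 31-day gap, are unaffected. The other is that patients would be dropped from the PP set. Under SAP 3.3 and 4.2 that is decided at a blinded data review, with listings that flag estimated dates, so exclusion is possible but not a product of the date rule. The FAS primary analysis does not use medication dates.

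The mismatch between SAP 4.5 and Protocol 10.9 holds regardless of any date assumption.

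**What to change.** 1. Add to SAP 4.1.5: *A medication documented in the eCRF as stopped before the first IMP dose is classed as prior, and its imputed stop date is the earlier of the month or year end and the day before first dose. All other medications keep the worst-case rule.* The limit must be the day before first dose, and it must be confined to documented stops. A blanket limit would relabel as prior some drugs that were really taken during treatment.

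2. In SAP 4.5, restore the summary of prior as well as concomitant medications, by treatment group at ATC levels 2 and 4, in line with Protocol 10.9. SAP 3.4 can then stay as it is on this point.

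The cost is one sentence of SAP text and one extra table. The small downside is reliance on the site's record that the drug had been stopped.

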4.2. Disposition of patients

The number of patients screened, the number of patients randomized and the number of patients in each analysis population will be summarized. The reasons for exclusion from each analysis population will be summarized for all patients randomized. The reasons for non-eligibility for randomization, i.e. the violated inclusion or exclusion criteria will be listed for all non-randomized patients by visit.

Major protocol deviations (leading to the exclusion from the PP) and minor protocol deviations (not leading to the exclusion from the PP) will be summarized for the safety population. The determination of major and minor protocol deviations will be performed during the blind data review meeting documented in the blind data review meeting minutes, which will be finalized prior to unblinding of the treatment group for the main analysis of data of the double-blind treatment. In addition a listing of subjects excluded from PP population and pharmacokinetic populations will be provided with specification of reason for exclusion for analysis.

The number of patients who completed the study and the number of patients who terminated the study early will be summarized in frequency tables for the safety, the FAS and the PP populations.

The timing of early termination will be summarized for each study month for the safety, the FAS and the PP populations.

Consolidated Standards of Reporting Trials (CONSORT) diagram (Moher et al. 2001) will be used to present abovementioned data in a graphical form.

